### 4.1 Analysis Sets

#### 4.1.1 Safety Analysis Set

The safety analysis set consists of all patients who receive ADCT-301.

#### 4.1.2 DLT-evaluable Analysis Set (Part 1)

The DLT-evaluable analysis set consists of patients who complete two cycle of ADCT-301 if enrolled prior to protocol amendment 4 and patients who complete one cycle of ADCT-301 if enrolled after protocol amendment 4. The patients with completed DLT information will be included even if they discontinue early before the end of cycle 2 or cycle 1 respectively.

#### 4.1.3 Efficacy Analysis Set

The efficacy analysis set consists of patients who receive at least one dose of ADCT-301 with a valid baseline and at least one valid post-baseline disease assessment or patients who have documented progression of disease or death at any time after the first dose of study.

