5.1.5 End of Treatment Visit

The following procedures will be performed as soon as possible after decision to discontinue the study drug and prior to initiation of anticancer treatment:

- Serum or urine pregnancy test.
- Physical examination, including neurological examination and including whole body skin assessment. Whole body skin assessment does not have to be performed by a dermatologist; however, any unexplained lesion will be referred to a dermatologist for further evaluation and skin biopsy, if clinically warranted. The examination must include a determination if the patient has had any infection. At the discretion of the investigator, evaluation of any reported infection must be conducted to rule out infection with a microorganism that may be associated with autoimmune or neurological disease(s) as specified in the exclusion criteria.
- Vital sign measurements.
- ECOG performance status.
- Weight
- Disease assessments:
 - Patients who already have documented objective disease progression do not need to have assessments repeated.
 - Patients who do not already have documented objective disease progression will have assessments performed at the end of treatment visit if the most recent disease assessment was > 9 weeks prior to the end of treatment visit.
- Hematology.
- Coagulation panel.
- Biochemistry.
- Urinalysis.
- Additional renal function studies.
- 12-lead ECG.
- Sample collection for central laboratory assessment of PK, [REDACTED], ADA, and [REDACTED]
- Sample collection and shipment for PBMC subset analysis (only in Study Part 2).
- AE collection (collected until 84 days [12 weeks] after last dose of study drug).
- Concomitant medication use.

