5.1.6 Long-term Follow-up

Patients who discontinue treatment for any reason other than objective disease progression will continue to be followed with scans approximately every 12 weeks from the last tumor assessment until disease progression, or initiation of new anticancer treatment. If a patient discontinues treatment for a hematopoietic stem cell transplant, the frequency of imaging will be as per the transplant center standard of care.

After documentation of disease progression or start of new anticancer treatment, patients will be contacted by telephone approximately every 12 weeks for up to 12 months after the last dose of study drug to collect survival information.

Blood Sample Collection and Adverse Event Monitoring During Long-Term Follow-up

For all patients, PK and ADA blood sample collection will be performed 12 weeks (\pm 1 week) following the last dose of ADCT-301, unless a new anticancer treatment has been initiated.

Patients who test positive for ADAs may be requested to supply additional ADA samples.

For all patients, collection of AEs and SAEs will continue for 12 weeks after the last dose of study drug or initiation of new anticancer treatment (see [Section 7.3.2.2](#)).

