8.4 Analysis Sets

Five analysis sets will be used in this study:

- The Safety analysis set consists of all patients who receive study drug
- The DLT-evaluable analysis set consists of all patients in Part 1 who receive study drug and excludes patients who discontinue from the study during the first 21-day cycle without experiencing a DLT.
- The Efficacy analysis set will consist of all patients with valid baseline data who receive at least 2 doses of study drug or who have documented progression of disease at any time after the first dose of study drug. Patients who do not have a post baseline assessment due to early clinical progression, toxicity, or death will also be included.
- The PK analysis set consists of all patients who receive study drug and have sufficient concentration data for PK analysis.

- The pharmacodynamic analysis set consists of all patients who receive study drug and have sufficient concentration data for pharmacodynamic analysis.

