### **3.3 Modifications to the statistical section of the protocol**

The efficacy analysis set was defined in the protocol as all patients with valid baseline data who receive at least 2 doses of study drug or who have documented progression of disease at any time after the first dose of study drug. The efficacy analysis set is updated in the SAP to include all patients who have received at least one dose of ADCT-301 with a valid baseline and at least one valid post-baseline disease assessment or patients who have documented progression of disease or death at any time after the first dose of study drug.

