## 4 Statistical methods

All analyses use SAS® version 9.4 or higher. Summary tables will be organized by each dose level; if some dose levels have few patients, then dose levels could be combined into dose ranges. All available data will be used in the analyses, and important data will be included in data listings, sorted by dose level, patient, and by visit within patient. Missing data will not be imputed, except via censoring in survival analyses and as otherwise specified.

Unless otherwise noted, categorical data will be presented using counts and percentages, with the number of patients in the analysis set by treatment group as the denominator for percentages. Percentages will be rounded to one decimal place, except 100% will be displayed without any decimal places and percentages will not be displayed for zero counts. Continuous data, unless otherwise noted, will be summarized using the number of observations (n), mean, standard deviation (std), median, minimum, and maximum. Minima and maxima will be rounded to the precision of the original value, and means, medians, and 95% confidence intervals (CIs) if presented will be rounded to 1 decimal place greater than the precision of the original value. The std will be rounded to 2 decimal places greater than the precision of the original value, up to a maximum of 3 decimal places.

No hypothesis testing will be performed in this study.

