#### **4.9.1 Overall Response Rate**

Overall response rate is defined as the proportion of patients who achieve either CR or PR as best overall response as assessed by investigators according to the Lugano Classification criteria or Global Response Score Grading Scales for CTCL patients before the start of subsequent anticancer therapy or procedure.

The order of overall response category is: CR, PR, SD, NE, PD (including disease recurrence/relapse). The overall response category will be derived based on response assessment performed on or before the start of subsequent anticancer therapy/procedure. Patients without documented subsequent anticancer therapy and/or with missing start date of anticancer therapy will be considered as not having received subsequent anticancer therapy. If a patient only has one valid disease assessment which is SD, and the assessment is within 35 days after the first dose, the overall response for this patient will be considered as NE.

The overall response rate and the corresponding 95% two-sided exact confidence interval at each dose level will be presented. Subgroup analysis may be provided if relevant.

Percent change from baseline in the sum of product of diameters (SPD) for target lesions for non-CTCL patients and mSWAT total score for CICL patients will be presented for available data in the efficacy analysis set by dose level. These data will also be displayed as a waterfall plot, with vertical bars representing the sorted values of best percent reduction for each patient.

Tumor response and lesion measurement (or mSWAT) will be listed by assessment visit.

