### **4.9.5 Overall Survival**

Overall survival is defined as the interval between the date of first dose and the date of death from any cause. Patients who are known to be alive as of their last known status will be censored at their date of last contact. Patients who are lost to follow-up will be censored at the date the patient is last known to have been alive. The last confirmed alive date is the latest of the following: study visit date, telephone contact date, end of study last confirmed alive date, follow-up systemic (anticancer) therapy end date or start date (if ongoing or end date is missing), local or central radiologist scan date, or other date in the clinical database.

OS will be estimated and displayed by dose levels for the efficacy analysis set using Kaplan-Meier methods (SAS® PROC LIFETEST). A Kaplan-Meier plot will be presented.

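### SAP efficacy set admits unassessed patients only on progression or death, which biases OS down and, if ORR is run on the same set, ORR up

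*SAP*

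**What the plan says.** **Protocol 8.4** has three ways into the efficacy set. The first is valid baseline data with at least two doses, with no scan required. The second is documented progression at any time after the first dose. The third reads: "Patients who do not have a post baseline assessment due to early clinical progression, toxicity, or death will also be included".

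**SAP 4.1.3** requires at least one dose and a valid baseline, with "at least one valid post-baseline disease assessment or patients who have documented progression of disease or death at any time after the first dose". The two-dose route and the toxicity route are both gone.

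**SAP 3.3** declares that the set was changed. Its account of the old definition begins "The efficacy analysis set was defined in the protocol as all patients with valid baseline data who receive at least 2 doses of study drug" and goes on to the progression route, but leaves out the protocol sentence that contains toxicity. The loss of the two-dose route can be seen from SAP 3.3; the loss of the toxicity route cannot.

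**Where the set is used.** For survival, SAP 4.9.5 states: "OS will be estimated and displayed by dose levels for the efficacy analysis set using Kaplan-Meier methods". For response, SAP 4.9.1 states: "The overall response rate and the corresponding 95% two-sided exact confidence interval at each dose level will be presented", and names no set. The general rule in SAP 4 is that percentages are computed "with the number of patients in the analysis set by treatment group as the denominator for percentages". The efficacy set is therefore the natural reading for ORR, but the SAP does not say so.

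**The concern.** The patients at issue stop treatment early without documented progression, for example because of toxicity or withdrawal. They then start new therapy, withdraw or are lost before any further scan.

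The visit schedule allows this. The first on-treatment assessment is at about 6 weeks (Protocol 7.1). An End of Treatment scan is required only "if the most recent disease assessment was > 9 weeks prior to the end of treatment visit". After that, patients are "followed with scans approximately every 12 weeks from the last tumor assessment until disease progression, or initiation of new anticancer treatment". Counted from a screening scan on Day -28 to -1, 12 weeks later is about Day 56 to 84. Anyone who leaves or switches therapy before then may have no valid post-baseline scan.

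Under SAP 4.1.3 such a patient is outside the set while alive and enters it once death is recorded. For OS, membership of the set then depends on the outcome being estimated. For ORR, patients who cannot be responders leave the denominator, and they return as non-responders when they die, so the reported rate can move with the data cut. Both endpoints are shown by dose level. Part 2 cohorts are about 10 patients (Protocol 8.3), so one exclusion is visible: 3/10 = 30.0% becomes 3/9 = 33.3%.

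**Working it through.** The plan gives no efficacy figure to reproduce. It also gives no share of unassessed patients, so every share below is an assumption.

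**Inputs (all assumed)**
- f, the share of treated patients with no post-baseline assessment and no documented progression: 5%, 10%, 15%.
- d, the share of those who die by 12 months: 40%, 60%, 80%.
- 12-month survival in assessed patients: 40%.
- True ORR in all treated patients: 30%.

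**Direction of the OS bias.** Every patient removed is alive, so every one is censored. Removing a censored patient can only shrink the risk sets, so each Kaplan-Meier factor falls or stays the same. In 20,000 random small samples, dropping one censored patient never raised the curve. The direction needs no assumption about shares.

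**OS at 12 months, survival fully followed**
- All treated: 0.40(1 − f) + f(1 − d)
- SAP set: 0.40(1 − f) / [(1 − f) + f·d]

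At f = 10% and d = 60%:
- All treated: 0.36 + 0.04 = 40.0%
- SAP set: 0.36 / (0.90 + 0.06) = 37.5%

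| f | d | All treated | SAP set | Shift (points) |
|---|---|---|---|---|
| 5% | 40% | 41.0% | 39.2% | 1.8 |
| 5% | 60% | 40.0% | 38.8% | 1.2 |
| 5% | 80% | 39.0% | 38.4% | 0.6 |
| 10% | 40% | 42.0% | 38.3% | 3.7 |
| 10% | 60% | 40.0% | 37.5% | 2.5 |
| 10% | 80% | 38.0% | 36.7% | 1.3 |
| 15% | 40% | 43.0% | 37.4% | 5.6 |
| 15% | 60% | 40.0% | 36.2% | 3.8 |
| 15% | 80% | 37.0% | 35.1% | 1.9 |

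**OS if survival follow-up of the unassessed ends at month 3.** Protocol 4.1 stops survival follow-up when new therapy starts, while 5.1.6 continues it, so both cases matter. Take exponential survival Sa(t) in assessed and Su(t) in unassessed patients.
- All treated: [(1 − f)Sa(3) + f·Su(3)] × 0.40 / Sa(3)
- SAP set: 0.40(1 − f) / [(1 − f) + f(1 − Su(3))]

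At f = 10% and d = 60%, Su(3) = 0.40^0.25 = 0.795. The SAP set gives 0.36 / (0.90 + 0.0205) = 39.1%, against 40.0%. Over the same grid the shift is 0.4 to 1.5 points.

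**ORR, if run on this set.** Excluded patients have no valid assessment and cannot be responders, so reported ORR = true ORR / (1 − m), with m = f(1 − d).
- Central case: m = 0.10 × 0.40 = 4%; 30 / 0.96 = 31.3%.
- Range: m = 1% gives 30.3%; m = 9% gives 33.0%.
- Effect of the data cut, central case with a constant death rate: 20.5% of the unassessed have died by month 3, so m = 7.95% and ORR reads 32.6%. By month 12 it reads 31.3%. No response has changed.

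**PFS.** SAP 4.9.4 censors patients with no post-baseline assessment on Day 1. Adding 6 such patients to 60 leaves the Kaplan-Meier curve unchanged (maximum difference 0.0), so PFS is not affected.

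**The case against.** **Size.** The full-follow-up OS figures fit poorly with patients who withdraw or are lost, since those patients have no later survival data. Full follow-up applies only to those who switch therapy, and only if Protocol 5.1.6 governs over 4.1. This stands: for withdrawn or lost patients the range of 0.4 to 1.5 points is the likelier one, and if follow-up ends at month 2 it is 0.3 to 1.0. The 5.6-point extreme also supposes that unassessed patients survive better (60%) than assessed ones (40%). Where they do equally or worse, the full-follow-up maximum is 3.8 points.

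**Group size.** The excluded group may be small. Clinical progression recorded at the end of treatment counts in the efficacy endpoints, and patients who stop for toxicity continue to be scanned. This is fair, and the documents do not settle it.

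**Comparator.** The shifts are measured against all treated patients and not against the protocol's set, which itself had outcome-dependent entry through progression and also left out some one-dose patients. The SAP set is wider in one respect, because a one-dose patient with a valid scan now enters. These points limit how much can be blamed on the change of definition. They do not remove the dependence of OS entry on death.

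**Consequence.** SAP 4 plans no hypothesis testing, and precision is low: the exact 95% interval is about 7% to 65% at 3/10 and 19% to 43% at 18/60. SAP 4.2 tabulates set sizes by dose level, so the exclusions can be counted. This limits the importance, but a table of set sizes does not correct the estimates. The ORR part is conditional on the set used; the unnamed denominator is a gap in any case.

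**Conclusion.** The concern holds. Followed as written, SAP 4.1.3 and 4.9.5 give an OS estimate that is biased down whenever an unassessed survivor is excluded. ORR is biased up by 1/(1 − m) if it uses the same set. The direction is certain; the size rests on assumed shares. On those assumptions OS shifts by 0.6 to 5.6 points with full 12-month follow-up, or by 0.4 to 1.5 points if follow-up of the unassessed ends at month 3. A true ORR of 30% would read 30.3% to 33.0%. The effect is on reported secondary estimates and not on a decision rule. It should be fixed, because the estimate is wrong as specified and the full change from the protocol is not disclosed.

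**What to change.** 1. In SAP 4.9.1, name the analysis set for ORR.
2. Report ORR and OS on all treated patients, using the existing safety set (SAP 4.1.1). For ORR, count patients with no valid baseline or no post-baseline assessment as NE non-responders in the denominator.
3. Keep the current SAP 4.1.3 set as a response-evaluable sensitivity analysis.
4. In SAP 3.3, give the full Protocol 8.4 definition and state that the toxicity route was removed.

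PFS needs no change on this account. The cost is SAP wording only, with no new data. Compared with the current set, ORR becomes slightly less favourable and OS slightly more favourable.

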## 4.2 Patient Disposition

The number and percentage of patients enrolled and treated in the study will be presented along with the number and percentage of patients in each analysis set for each dose level. In addition, for the safety analysis set, the number and percentage of patients who withdrew from study treatment and who discontinued the study for each reason will be tabulated for each dose level.

Patient disposition data will be listed.

### 4.3 Protocol Deviations

The number and percentage of patients with any important clinical study report (CSR) reportable protocol deviation will be summarized overall and by type of deviation. The pre-defined important CSR reportable protocol deviations are listed below; in addition, any other protocol deviations deemed by ADCT medical to be important CSR reportable deviations will be included in the summary.

1. Patient entered the study even though they did not satisfy the entry criteria
2. Patient received a prohibited concomitant treatment during the study
3. Patients who met criteria for mandatory withdrawal of study drug during the study but did not have study drug withdrawn. The criteria for mandatory withdrawal of study drug included:
  - Any patient who experiences a Grade 3 or higher hypersensitivity (Appendix 13.4 in the protocol) reaction, regardless of premedication, during any cycle of treatment.
  - Any patient who experiences a recurrent Grade 3 or 4 toxicity, excluding hematological toxicity.
  - Any patient who requires a dosing delay >21 consecutive days from the planned Day 1 dosing at any time during treatment (except in case of potential patient benefit, which must be approved by the Sponsor).
4. Patient who received the wrong treatment or incorrect dose. For example,
  - Actual dose of study drug was more than 15% greater than protocol defined planned dose level.
  - Patient started next cycle less than 18 days later after Day 1 of the most recent treatment cycle.

Important protocol deviations will be listed.

### 4.4 Demographic and Baseline Characteristics

Demographic and baseline characteristics will be tabulated for the safety analysis set by dose level. Variables include the following:

- Sex (female, male)
- Race (white, black or African American, Asian, American Indian or Alaska native, native Hawaiian or other Pacific Islander, other)
- Ethnicity (Hispanic or Latino, not Hispanic or Latino)
- Age (years)
- Age group (<55,  $\geq 55$  - < 65,  $\geq 65$  - < 75,  $\geq 75$  years)
- Height (cm)
- Weight (kg)
- Body mass index (kg/m^2)
- Eastern Cooperative Oncology Group (ECOG) performance status

Demographic and baseline characteristics data will be listed.

### 4.5 Cancer History and Medications History

Cancer history will be presented for the safety analysis set by dose level. Cancer history will include the following variables:

- Duration since diagnosis
- Disease diagnosis (non-Hodgkin lymphoma : T-cell lymphoma, B-lymphoma ; Hodgkin lymphoma)
- Disease diagnosis subtype (for non-Hodgkin lymphoma: diffuse large B-cell lymphoma, follicular lymphoma, mucosa-associated lymphatic tissue lymphoma/extranodal marginal zone B-cell lymphoma, small cell lymphocytic lymphoma/chronic lymphocytic leukemia, mantle cell lymphoma, mediastinal [thymic] large B-cell lymphoma, lymphoplasmacytic lymphoma and Waldenstrom macroglobulinemia, nodal marginal zone B-cell lymphoma, splenic marginal zone lymphoma, intravascular large B-cell lymphoma, primary effusion lymphoma, Burkitt lymphoma-Burkitt leukemia, lymphomatoid granulomatosis, peripheral T-cell lymphoma not otherwise specified, cutaneous T-cell lymphoma [Sézary], cutaneous T-cell lymphoma [mycosis fungoides], anaplastic large cell lymphoma, angioimmunoblastic T-cell lymphoma, lymphoblastic lymphoma [can sometimes be a B-cell subtype], NK-cell lymphoma, other; for Hodgkin lymphoma (classical Hodgkin lymphoma): nodular sclerosis classical Hodgkin lymphoma, lymphocyte-rich classical Hodgkin lymphoma, mixed cellularity classical Hodgkin lymphoma, lymphocyte-depleted classical Hodgkin lymphoma, other)
- Stage of disease (NHL and HL, non-CTCL; Stage I, II, III, IV; constitutional symptoms A, B; Subtype E, X, S)
- Stage of disease (CTCL, IA, IB, IIA, IIB, IIIA, IIIB, IVA1, IVA2, IVB)
- Cytogenetic analysis (results available yes, t [11;14], t [11q], +12, del [11q], del [13q], del [17p], t [14;18], t [8; 14], other)
- Immunophenotypic analysis (results available yes; IgVH status mutated, unmutated, not applicable; CD5, CD10, CD19, CD20, CD21, CD23, CD43, BCL1, BCL2, BCL6, CYCLIN D1, ZAP70 negative, positive, not done)

Prior anticancer procedure or therapy will include the following variables:

- Number of lines of therapy/ regimens per patient
- Any prior surgeries for the current malignancy (yes, no)
- Any prior radiotherapy for the current malignancy (yes, no)
- Any prior systemic therapy for the current malignancy (yes, no)
- Type of systemic therapy (Brentuximab Vedotin, Checkpoint inhibitor, other)
- Reason for stopping therapy (progression, toxicity, other)
- Best response (complete response [CR], partial response [PR], stable disease [SD], progressive disease [PD], not evaluable [NE])
- Any prior stem cell transplant (yes, no)
- Type of transplant (allogenic, autologous, both, other)

Medical and cancer history data will be listed. Results of cytogenetic analysis and immunophenotypic analysis will be listed. CD25 expression level data will be listed if available. Tumor tissue biopsy collection will not be listed, but will be contained in datasets.

Prior anticancer surgery, radiotherapy, systemic therapy, and stem cell transplant data will be listed.

## **4.6 Prior or Concomitant Medications (other than anticancer therapies)**

All medications taken within 14 days before dosing and until the end of the study are to be reported in the CRF pages.

All medications will be coded using the World Health Organization-Drug Dictionary (WHO-DD) and presented by dose level for the safety analysis set.

- Prior medications are those the patient used prior to first investigational product (IP) intake. Prior medications can be discontinued before first dosing or can be ongoing during the treatment phase.
- Concomitant medications are any treatments received by the patient concomitantly to any IP(s), from first dose (or start of the observation period) to the last dose + 30 days. A given medication can be classified both as a prior medication and as a concomitant medication. Concomitant medications do not include medications started 30 days after the last dose.

Any technical details related to computation, dates, and imputation for missing dates are described in Section 6.

Prior medications will be listed together with concomitant medications.

